6.3. Study Intervention Compliance

- When participants are dosed at the site, they will receive study intervention directly from the Investigator or designee, under medical supervision. The date and time of each dose administered in the clinic will be recorded in the source documents. The dose of study intervention and study participant identification will be confirmed at the time of dosing by a member of the study site staff other than the person administering the study intervention.
- If participants are not dosed at the site at the Week 2 (Day 15), Week 4 (Day 29) and/or Week 8 (Day 57) visit(s), the time the dose is taken on those visit days must be confirmed by the site staff through follow-up with the participant, and time and date of dose information will be recorded in the CRF.
- When participants self-administer study intervention(s) at home, compliance with study treatment will be assessed by reviewing the information from the returned diary cards at the study visits, and documenting compliance in the source documents and CRF.
- A record of the number of study treatment tablets dispensed to and taken by each
 participant must be maintained and reconciled with study intervention and
 compliance records. Intervention start and stop dates, including dates for intervention
 delays, will also be recorded in the CRF.

6.4. Concomitant Therapy

Any medication or vaccine (including over-the-counter or prescription medicines, vitamins, and/or herbal supplements or other specific categories of interest) that the participant is receiving at the time of enrolment or receives during the study must be recorded along with:

- reason for use
- dates of administration including start and end dates
- dosage information including dose and frequency

Any allowable medication should be stably maintained prior to enrolment to the study. Usage should be approximately stable and consistent throughout the study intervention and follow-up. The Medical Monitor should be contacted if there are any questions regarding concomitant or prior therapy.

Selected medications for the treatment of psoriasis may be taken, with specific requirements listed in Table 1, and as long as they are not prohibited (Section 6.4.1).

Table 1 Specific Requirements for Permitted Medications During the Study

Therapy	Requirement
Emollients (excluding those containing salicylic acid)	 Omit on day of study visits until after all skin assessments have been performed. May be used at other times.
	,
Low or least potent (Class 6 or 7) topical corticosteroids ¹	 Only on palms, soles, face, and intertriginous areas
	Hydrocortisone 1% and hydrocortisone acetate 1% are the only topical corticosteroids permitted
	Omit on day of study visits until after all skin assessments have been performed.
Medicinal shampoos that contain tar and/or salicylic acid (but not corticosteroids)	Permitted at any time on scalp area.

^{1.} Usage should be approximately stable for 14 days prior to dosing.

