6.4.1. Prohibited Medicines

Participants must abstain from taking prescription or non-prescription drugs (including vitamins and dietary or herbal supplements) within 7 days (or 14 days if the drug is a

2019N420902_03 **CONFIDENTIAL** 208022

potential enzyme inducer) or 5 half-lives (whichever is longer) before the start of study intervention until completion of the follow-up visit, unless the medication will not interfere with the study, in the opinion of the Investigator and sponsor.

Table 2 lists prohibited medications for defined periods of time before and during the study until after the follow-up visit (Day 113).

Participants who start prohibited medications or therapies as a treatment for PsO or other reasons during the study may be withdrawn from study treatment for safety reasons. If in any doubt, Investigators are advised to discuss medications with the medical monitor.

Table 2 Prohibited Medications

Prohibited Therapy	Washout Period (from before D1 until follow-up)	
Biologic Agents (including but not limited to: adalimumab, etanercept, infliximab, certolizumab, ustekinumab, guselkumab, ixekizumab, secukinumab, risankizumab)	4 weeks for etanercept; 8 weeks for infliximab; 12 weeks or 5 half-lives (whichever is longer) for other biologics	
Oral retinoids (including but not limited to: acitretin or isotretinoin)	12 weeks	
Systemic immunosuppressive or immunomodulating agents. (including but not limited to: cyclosporin, interferon, methotrexate, apremilast)	8 weeks	
Systemic corticosteroids or adrenocorticotropic hormone (ACTH) analogs	4 weeks	
Phototherapy (PUVA, UVB or self-treatment with tanning bed)	4 weeks	
Topical Treatments (including but not limited to: corticosteroids [low potency corticosteroids permitted for certain areas, see permitted medications], immunomodulators, anthralin [dithranol], Vitamin D derivatives, retinoids, or coal tar [used on the body])	2 weeks	

Prohibited Therapy	Washout Period (from before D1 until follow-up)	
 Live or attenuated Vaccinations If indicated, non-live vaccines (e.g. inactivated influenza vaccines) may be administered whilst receiving GSK2982772 based on an assessment of the benefit: risk (e.g. risk of decreased responsiveness). 	30 days for live or attenuated vaccinations	
• Investigators are expected to follow local and/or national guidelines with respect to vaccinations, including against pneumococcus and influenza, in participants with PsO.		

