8.1. Efficacy Assessments

8.1.1. Clinical Disease Assessments

8.1.1.1. Psoriasis Area Severity Index (PASI)

Psoriatic lesions will be assessed using the PASI scoring system [Fredriksson, 1978]. Erythema, induration, and scale are each graded on a 5-point scale (0-4), and the % BSA affected is scored on a 7-point scale (0-6) for each of the 4 specified body regions (head, upper extremities, trunk, and lower extremities). The body region scores are each multiplied by a weighted factor; and the sum of the region scores give the overall PASI score. Higher scores indicate more severe disease. PASI is a static measurement made without reference to a previous score (see SRM for full details).

The PASI assessment will be performed by the Investigator or suitably trained delegate, and whenever possible, the PASI assessments for an individual participant should be completed by the same assessor at all time points.

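### Table 1 of the protocol allows tar or salicylic acid scalp shampoo just before skin scoring but holds its other two products, a small and avoidable source of noise in PASI

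*Protocol*

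**What the plan says.** Table 1 in Protocol Section 6.4 has three rows. The emollient row and the row for low-potency topical corticosteroids (1% hydrocortisone or its acetate) both carry the instruction "Omit on day of study visits until after all skin assessments have been performed". The third row covers medicinal shampoos containing tar, salicylic acid or both, and its only condition is "Permitted at any time on scalp area".

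Three nearby provisions bear on this:
- The emollient row leaves out products containing salicylic acid, and Table 2 in Section 6.4.1 prohibits coal tar on the body only.
- Section 6.4 says of allowable medication in general: "Usage should be approximately stable and consistent throughout the study intervention and follow-up".
- A footnote, "Usage should be approximately stable for 14 days prior to dosing", is marked on the corticosteroid row alone.

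Protocol Section 8.1.1.1 makes scale one of three signs graded 0 to 4 and the head one of four regions. Section 8.1.1.3 has sIGA judged over the entire body. PASI of at least 12 is an entry criterion at Screening and Baseline (Section 5.1). PASI75 at Week 12 is the primary endpoint, and SAP Section 1.2.1 applies no rounding when responders are derived.

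**The concern.** The hold on emollients and hydrocortisone shows that the plan regards same-day topical use as able to disturb scoring. The shampoo row has no such protection, and the protocol does not say why.

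The general stability sentence limits changes in how much a participant uses. It does not fix the interval between use and scoring. Someone who shampoos weekly can be perfectly stable and still be scored several days after a wash at one visit and an hour after it at another. If a wash alters visible scalp scale, part of the recorded change in PASI reflects that interval and not the disease.

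At stake is some avoidable measurement noise in a responder endpoint with a hard cut, in a trial planned at 14 and 7 participants.

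**Working it through.** The documents state no figure on this point, so there is nothing to reproduce. The check has two parts.

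**1. Does any text control use just before scoring?** The shampoo row sets no limit on time of day. The stability sentence concerns usage over the study, and the 14-day footnote is not marked on the shampoo row. Section 6.4 requires the reason, dates, dose and frequency of each medication to be recorded, but not the time of use relative to an assessment. Full PASI instructions are deferred to the Study Reference Manual, which is not among the documents. Nothing available supplies a hold.

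**2. How large could the effect be?**

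Inputs from the documents: scale graded 0 to 4, area scored 0 to 6, entry PASI of at least 12, PASI75 cut at 25% of baseline.

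Assumptions, none given in the documents:
- Head weight 0.1. Section 8.1.1.1 refers only to a weighting factor, so 0.25 (four equal weights) is shown as the upper end.
- Region score equal to the area score times the sum of the sign grades.
- Head area score 2 to 4, and a change of 1 to 2 grades in head scale from use shortly before scoring.

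Formulas:
- Shift in PASI = weight × area score × change in scale grade
- Shift in percentage improvement, if it occurs at Week 12 = 100 × shift ÷ baseline PASI
- Movement of the PASI75 cut, if it occurs at Baseline = 0.25 × shift

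| Weight | Area, grades | Shift in PASI | Week 12, baseline 12 | Week 12, baseline 20 | Cut moves by, if at Baseline |
|---|---|---|---|---|---|
| 0.1 | 2, 1 | 0.1 × 2 × 1 = 0.2 | 1.7 pp | 1.0 pp | 0.05 |
| 0.1 | 4, 2 | 0.1 × 4 × 2 = 0.8 | 6.7 pp | 4.0 pp | 0.2 |
| 0.25 | 2, 1 | 0.25 × 2 × 1 = 0.5 | 4.2 pp | 2.5 pp | 0.125 |
| 0.25 | 4, 2 | 0.25 × 4 × 2 = 2.0 | 16.7 pp | 10.0 pp | 0.5 |

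(pp = percentage points of PASI improvement)

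Who could be reclassified, at weight 0.1 and baseline 12? The cut is 0.25 × 12 = 3.0. Use before the Week 12 scoring could turn a non-responder into a responder only if the score without it lies above 3.0 and at or below 3.2 (small case) or 3.8 (large case). That means an improvement of at least 1 − 3.2/12 = 73.3%, or 1 − 3.8/12 = 68.3%, but under 75%. The large case also needs at least 0.8 of that remaining score to come from head scale alone.

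Use on the day of Baseline works the other way: it lowers the baseline score and makes response slightly harder to reach. At entry, a participant whose score without same-day use lies from 12.0 to just under 12.2 (or 12.8) would be recorded below 12.

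**The case against.** The strongest reply is that Table 1 sets requirements product by product and does not contradict itself. The scalp allowance is explicit and fits Table 2, which restricts coal tar only on the body. That stands: the gap is an unexplained difference in timing conditions, not a conflict over what is permitted.

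Several stronger readings are tempting, and the documents do not support them:
- *That shampoo use goes unrecorded.* Section 6.4 requires over-the-counter products to be recorded. Only same-day timing is not asked for.
- *That the shampoos are known to remove scale.* No section says so. The omission of salicylic acid emollients is merely consistent with it.
- *That the treatment comparison is biased.* Allocation is randomised and double-blind, and usage is meant to be stable, so the effect is non-differential in expectation. Chance imbalance is possible with 14 and 7 participants, but that is noise.
- *That every other skin product is held.* This is true within Table 1 only. Section 5.3.3 advises sunscreen and lip balm with no hold.
- *That the effect is large because 0.8 is 27% of the 3.0 points allowed.* The ratio is arithmetically right, but it takes the lowest permitted baseline and the larger assumed shift. On the scale of the endpoint it is 6.7 percentage points.
- *That one reclassified participant moves the active rate by 1/14 = 7.1 points or the placebo rate by 1/7 = 14.3.* This holds for any measurement error in a trial of this size and says nothing about shampoo.

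The number of participants who will use such shampoos is unknown, and a visit-preparation instruction may exist in the Study Reference Manual. If one does, it would need to be squared with the permission in Table 1.

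**Conclusion.** The point holds as a minor one. Table 1 leaves one of its three products without the condition that protects scoring from same-day use, gives no reason, and no other available text closes the gap.

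The likely consequence is a small amount of non-differential noise in PASI and PASI75. An effect on sIGA is possible, but the documents give no basis for sizing it. With a head weight of 0.1, the shift at Week 12 is 1.7 to 6.7 percentage points of improvement at a baseline of 12 and 1.0 to 4.0 at 20. Equal regional weights would make it 2.5 times larger. The effect through Baseline is a quarter as large in PASI points. It matters only for shampoo users close to the 75% cut or to the entry limit of 12.

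All of these sizes depend on the assumed weight, area score and grade change. A reader might infer a threat to the primary conclusion; the documents do not support that.

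**What to change.** Reconcile the three rows of Table 1 so that one visit-day assessment condition applies to all permitted topical products. It should cover every visit at which PASI, BSA or sIGA is scored: Screening, Day 1 to Day 113, and Early Withdrawal. This standardises the assessment; the permission to use the shampoo would otherwise stay as it is.

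If the sponsor has a reason to keep the exemption, state it in Section 6.4 and record at each scoring visit whether shampoo was used that day before the assessment. The noise can then at least be described.

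The cost is one line in Table 1, matching text in the participant instructions, and a delay of a few hours in shampooing on visit days. The alternative costs one additional item in the case report form.

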6.4.1. Prohibited Medicines

Participants must abstain from taking prescription or non-prescription drugs (including vitamins and dietary or herbal supplements) within 7 days (or 14 days if the drug is a

2019N420902_03 **CONFIDENTIAL** 208022

potential enzyme inducer) or 5 half-lives (whichever is longer) before the start of study intervention until completion of the follow-up visit, unless the medication will not interfere with the study, in the opinion of the Investigator and sponsor.

Table 2 lists prohibited medications for defined periods of time before and during the study until after the follow-up visit (Day 113).

Participants who start prohibited medications or therapies as a treatment for PsO or other reasons during the study may be withdrawn from study treatment for safety reasons. If in any doubt, Investigators are advised to discuss medications with the medical monitor.

Table 2 Prohibited Medications

Prohibited Therapy	Washout Period (from before D1 until follow-up)	
Biologic Agents (including but not limited to: adalimumab, etanercept, infliximab, certolizumab, ustekinumab, guselkumab, ixekizumab, secukinumab, risankizumab)	4 weeks for etanercept; 8 weeks for infliximab; 12 weeks or 5 half-lives (whichever is longer) for other biologics	
Oral retinoids (including but not limited to: acitretin or isotretinoin)	12 weeks	
Systemic immunosuppressive or immunomodulating agents. (including but not limited to: cyclosporin, interferon, methotrexate, apremilast)	8 weeks	
Systemic corticosteroids or adrenocorticotropic hormone (ACTH) analogs	4 weeks	
Phototherapy (PUVA, UVB or self-treatment with tanning bed)	4 weeks	
Topical Treatments (including but not limited to: corticosteroids [low potency corticosteroids permitted for certain areas, see permitted medications], immunomodulators, anthralin [dithranol], Vitamin D derivatives, retinoids, or coal tar [used on the body])	2 weeks	

Prohibited Therapy	Washout Period (from before D1 until follow-up)	
 Live or attenuated Vaccinations If indicated, non-live vaccines (e.g. inactivated influenza vaccines) may be administered whilst receiving GSK2982772 based on an assessment of the benefit: risk (e.g. risk of decreased responsiveness). 	30 days for live or attenuated vaccinations	
• Investigators are expected to follow local and/or national guidelines with respect to vaccinations, including against pneumococcus and influenza, in participants with PsO.		
Pgp Inhibitors (including but not limited to: amiodarone, azithromycin, clarithromycin, conivaptan, erythromycin, felodipine, itraconazole [FDA, 2012])	4 weeks	
Narrow therapeutic index (NTI) CYP3A4 substrates. (including but not limited to: alfentanil, astemizole, cisapride, fentanyl, pimozide, quinidine, sirolimus, terfenadine [FDA, 2012])	4 weeks	
Sensitive substrates of CYP2B6 (including but not limited to: bupropion)	4 weeks	
Sensitive substrates of CYP2C8 (including but not limited to: repaglinide)	4 weeks	
OAT3 inhibitors (including but not limited to: probenecid, teriflunomide)	4 weeks	

Paracetamol/acetaminophen, at licensed doses, is permitted for use. Other concomitant medication may be considered on a case by case basis by the Investigator, in consultation with the medical monitor if required.

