9.3. Populations for Analyses

The following populations are defined:

Population	Description
Screened	All participants who were screened for eligibility.
Enrolled	All participants who signed the ICF, passed screening and were eligible for randomisation (regardless of whether the participant went on to be randomised).
Randomised	All participants who were randomly assigned to study intervention in the study. Participant must have signed ICF and passed screening. Data will be reported according to the randomised study intervention.
Intent to Treat (ITT)	All randomised participants who received at least one dose of study treatment. Data will be reported according to the randomised study intervention.
Safety	All randomized participants who receive at least 1 dose of any study treatment. Data will be reported according to the actual study intervention received.
COVID-19	All participants in the Safety set who had a confirmed, probable or suspected COVID-19 case diagnosis.

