9.4.1. Primary Analyses

Efficacy analyses will be based on the ITT population unless stated otherwise in the SAP. The primary analysis will assess the difference in PASI75 response rates between GSK2982772 960 mg and placebo at Week 12. A Bayesian logistic regression analysis of the difference in PASI75 response rates at Week 12 will be conducted to calculate posterior probabilities that the true effect of GSK2982772 relative to placebo is greater than a range values of interest.

An informative prior will be used for the placebo arm to leverage relevant historical placebo data into the analysis. It is expected that this prior will be a Beta (3.5, 46.5)

distribution, giving the historical data an effective sample size of 50 participants. Further emerging placebo data may be incorporated into the prior distribution for the placebo arm prior to breaking the study blind. A non-informative prior will be used for the PASI75 response rate on GSK2982772.

Participants who discontinue early or have missing PASI data at any visit will be treated as PASI75 non-responders at that time point (regardless of their response at previous visits). Sensitivity analyses will be conducted to investigate the impact of this approach to handling missing data.

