1.2.2. Estimands

Estimands were not incorporated into the protocol for this study. The missing data handling rules are outlined in analysis sections.

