4.1.1. Definitions for Per Protocol Analysis Set

This study will not include a Per Protocol analysis set.

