5.2.2. Main analytical approach

The primary analysis will be produced for the ITT population.

The summary measure of interest is the difference in PASI75 response rates at Week 12 (Day 85) between GSK2982772 and placebo. Missing values will be imputed as non-responders.

The primary endpoint will be analysed using a Bayesian logistic regression model, details given in [Table 2](#). Summary statistics will be provided for the posterior distribution of the true difference in PASI75 response rate (GSK2982772 vs placebo) as well as posterior probabilities for a range of thresholds.

A non-informative prior will be used for the PASI75 response rate on GSK2982772 and covariates.

An informative prior will be used for the placebo response rate of the form: 90% weight on $Be(5.39, 69)$ and 10% on $Be(1/3, 1/3)$. The prior was derived from historical data from similar clinical trials using meta-analytic predictive prior (MAP) approach, the effective sample size is approximately 63 [[Schmidli, 2014](#)].

In the event that the placebo prior is different from what is presented here, this will be documented in the CSR.

Table 2 Statistical Analysis of Primary Endpoint

Endpoint(s)	

 PASI75 response at Week 12 (Day 85) 	
Analysis Method	
Bayesian Logistic Regression (using informative prior)	
Model Specification	
Outcome	$y_i = \text{Response (0/1) for participant } i$
Predictors	
 Treatment (categorical) Prior Biologic Use (categorical) Baseline PASI score (continuous) 
Unless stated otherwise the predictors (not including study treatment) will be centered around their estimated mean prior to inclusion in the model

Model	$y_i \sim \text{Ber}(p_i)$ $\text{logit}(p_i) = (\text{Treatment=Placebo}) \times \beta_1 + (\text{Treatment=GSK}) \times \beta_2 + (\text{Prior Biologic Use}^*) \times \beta_4 + (\text{Baseline PASI score}^*) \times \beta_5$
Prior distributions for coefficients (β)	β = fixed effect parameters associated to predictors 
 β_1: informative prior such that $\text{logit}^{-1}(\beta_1) \sim$ mixture of Betas* β_2: non-informative prior such that $\text{logit}^{-1}(\beta_2) \sim \text{Beta}(1/3, 1/3)$ Other β_k: non-informative priors of $N(0, SD=100)$ 
*Expected prior is a mixture of $Be(5.39, 69)$ and $Be(1/3, 1/3)$, weighted to 90% and 10% respectively. Final prior will be reported in the CSR.

Model Checking & Diagnostics	
See Section 5.1.1	

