5.2.3. Sensitivity analyses

Where informative priors have been used, a sensitivity analysis using vague priors (no historical borrowing) will also be produced.

Additional sensitivity analyses to assess the impact the missing data handling for binary data may be produced, such as using a LOCF approach to missing data.

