5.2.4. Supplementary analyses

A supplementary analysis where the primary analysis is repeated using the Modified ITT population may be produced to assess the treatment effect in subjects able to complete at least 4 weeks of treatment. A frequency table of PASI response using this population would also be produced.

Off-treatment PASI data, collected following treatment discontinuation prior to Week 12, may be used for additional supplementary analyses if available.

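### No rule says how an observed Week 12 PASI75 is scored when a participant starts a prohibited psoriasis therapy but stays on study treatment; this can bias the primary comparison.

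*Protocol*

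**What the plan says.** Protocol 6.4.1 and its Table 2 bar biologics, oral retinoids, systemic immunosuppressants and immunomodulators, systemic corticosteroids, phototherapy and most topicals until after the follow-up visit. For a participant who starts one anyway, the text is: "Participants who start prohibited medications or therapies as a treatment for PsO or other reasons during the study may be withdrawn from study treatment". The reason given for withdrawal is safety; how the response is then scored is not mentioned.

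The scoring rules are these:

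- Protocol 9.4.1: "Participants who discontinue early or have missing PASI data at any visit will be treated as PASI75 non-responders at that time point".
- SAP 5.2.2: "Missing values will be imputed as non-responders". SAP 5.3.2 applies the same missing-value rule to PASI50/90/100 and sIGA response.

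The primary population is ITT, defined in Protocol 9.3 as "All randomised participants who received at least one dose of study treatment" and reported by randomised arm. SAP 1.2.2 states: "Estimands were not incorporated into the protocol for this study". SAP 4.1.1 states: "This study will not include a Per Protocol analysis set".

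SAP 5.2.3 plans a vague-prior sensitivity analysis and adds: "Additional sensitivity analyses to assess the impact the missing data handling for binary data may be produced, such as using a LOCF approach". SAP 5.2.4 offers an optional analysis of Week 4 completers and adds: "Off-treatment PASI data, collected following treatment discontinuation prior to Week 12, may be used for additional supplementary analyses if available". Sections 5.3.3 and 5.3.4 plan no sensitivity or supplementary analyses for the secondary efficacy endpoints.

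**The concern.** Take a participant who starts a prohibited psoriasis therapy, is not withdrawn, and attends Week 12. That person has neither discontinued nor a missing PASI, so no non-response rule applies and the observed PASI75 counts. The therapies in Table 2 include established psoriasis treatments, so the response may be theirs and not the study drug's. With 14 and 7 participants, one reclassified case moves the crude rate by 1/14 = 7.1 points on active or 1/7 = 14.3 points on placebo. The stated objective is the efficacy of the study drug, and no estimand is declared under which responses after other therapy would legitimately count.

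**Working it through.** **Could another provision close the gap?**

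- Early-discontinuation rule (Protocol 9.4.1): reaches only those who stop.
- Missing-value rule (SAP 5.2.2, 5.3.2): does not reach an observed PASI.
- Vague-prior and LOCF sensitivity analyses (SAP 5.2.3): change the prior or the missing-data handling only.
- Week 4 completers and off-treatment PASI (SAP 5.2.4): neither isolates participants who stay on treatment after starting another therapy.
- Important protocol deviations (SAP 4.1): summarised, with no effect on scoring.
- OPS (SAP 1 and 1.2.1): holds endpoint derivations and data-handling conventions; not available here.

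**Inputs for the size.** Allocation 14:7 (SAP Table 2). Placebo prior 0.9 Be(5.39, 69) + 0.1 Be(1/3, 1/3) and active prior Be(1/3, 1/3) (SAP 5.2.2). Criteria Pr(difference >45%) >55% and Pr(difference >0) >97.5%, both listed in SAP Table 2 for the interim predictive probabilities. Design rates 7% and 7% + 55% = 62% (Protocol 9.2). The model covariates are left out because the documents give no values for them.

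**Formulae.** With a of 14 active responders, the active posterior is Be(1/3 + a, 1/3 + 14 − a). With y of 7 on placebo, each prior component Be(α, β) with weight w becomes Be(α + y, β + 7 − y), reweighted in proportion to w·B(α + y, β + 7 − y)/B(α, β). Then Pr(difference > d) = ∫ f_A(p) F_P(p − d) dp, evaluated numerically.

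**Plan's own figure.** Enumerating all 15 × 8 outcomes at 62% v 7% with the protocol's Beta(3.5, 46.5) placebo prior gives a 99.7% chance of meeting the 97.5% criterion, against about 99% stated. The SAP mixture gives 98.1%. The setup reproduces the design.

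**One case (SAP mixture prior).**

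| Active | Placebo | Pr(difference >45%) | Pr(difference >0) |
|---|---|---|---|
| 7/14 | 0/7 | 0.456 | 0.9998 |
| 8/14 | 0/7 | 0.661 | 0.9999 |
| 8/14 | 1/7 | 0.617 | 0.9992 |
| 8/14 | 2/7 | 0.551 | 0.9904 |
| 3/14 | 0/7 | 0.011 | 0.954 |
| 4/14 | 0/7 | 0.043 | 0.989 |

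One extra active responder crosses 55% in the first pair of rows and 97.5% in the last pair. The contaminated placebo responders at 8/14 cross neither threshold.

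**Why equal use is not neutral.** One more active responder raises the active posterior mean by 1/(14 + 2/3) = 6.8 points, nearly the crude 7.1. Going from 0/7 to 1/7 on placebo raises the placebo posterior mean from 0.0652 to 0.0818, or 1.7 points against a crude 14.3.

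**Illustration with assumed rates (not in the documents).** Suppose a share r of would-be non-responders starts such therapy and stays on treatment, and 60% of them reach PASI75. An underlying rate p becomes p + (1 − p) × r × 0.6.

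- No drug effect, r = 20% in both arms: 0.07 + 0.93 × 0.2 × 0.6 = 0.182 in each. The chance of meeting the 97.5% criterion rises from 1.2% to 15.3% (SAP prior). At r = 10% it is 7.0%.
- No drug effect, r = 20% on active only: 22.1%.
- Drug works (62%), r = 10, 20 or 30% on placebo only: the crude difference falls from 55.0 to 49.4, 43.8 or 38.3 points. The chance of meeting the 97.5% criterion falls from 98.1% to 93.8, 86.6 or 77.1%.

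**The case against.** The strongest reply has four parts.

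1. Such use may be rare: the therapies are barred and treatment lasts 12 weeks. This stands in part, since the documents give no frequency. A reader might infer that the primary comparison is biased; the documents support only that it can be.
2. A reader might infer that every such response is credited to the study drug, or that one case on either arm overturns the result. Neither holds. Analysis is by randomised arm, so a case on placebo is a placebo response, and in the placebo scenarios at 8/14 neither criterion is crossed. The active-arm crossings need results near a boundary; under the 62% design rate, exactly 7/14 has probability of about 14%. Both criteria are listed for the interim predictive probabilities, while SAP section 2 sets an estimation objective with no success threshold.
3. The OPS may hold a scoring rule. It cannot be excluded, so face-value scoring is how the protocol and SAP read, not a certainty. A rule this material to the primary endpoint still belongs in the SAP beside the missing-data rule.
4. Counting observed data regardless of other therapy is a recognised treatment-policy approach and fits an ITT set. That is a legitimate choice, but it has to be declared, and no estimand is. The protocol already applies composite non-response to early discontinuation, so extending it is the consistent choice for the responder endpoints.

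**Conclusion.** The gap is real in both documents. As they read, a participant who starts a prohibited psoriasis therapy, stays on study treatment and has a Week 12 PASI is scored at face value in the randomised arm. This can bias the primary comparison, upward for cases on active and toward zero for cases on placebo; equal use does not cancel, because the placebo prior absorbs most of the placebo rise and none of the active rise. One active case can decide either listed criterion near its boundary. The size rests on the SAP mixture prior, 14:7 and no covariates; the operating characteristics also rest on assumed rates of use and response. Frequency and net direction are unknown. This is a change that should be made before the first unblinded look.

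**What to change.** In SAP 5.2.2, and in 5.3.2 with Table 3, state that a participant who starts a Table 2 (Protocol 6.4.1) therapy with expected psoriasis efficacy before the Week 12 assessment is a non-responder from that date for the PASI and sIGA responder endpoints, whether or not the assessment is observed. Name the classes: biologic, systemic immunosuppressant or immunomodulator, oral retinoid, systemic corticosteroid, phototherapy, prohibited topical. Apply the rule whether the therapy was started for psoriasis or for another reason.

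Identify cases in a blinded review of concomitant medication before the interim analysis; Protocol 6.4 already requires reasons and dates. Report use by arm, and give as-observed scoring as a sensitivity analysis. For the Table 4 repeated-measures model, exclude PASI and BSA values after the start date as a sensitivity analysis only, because that exclusion relies on a missing-at-random assumption that is open to debate.

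The cost is a short SAP addition and one blinded review, with no new data. The observed response rate may be slightly lower, and brief topical use would count as non-response in the main analysis. No change to any withdrawal or treatment rule is proposed.
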